11.7.4 Regulatory Reporting Requirements for SAEs

- Prompt notification by the Investigator to the Sponsor of an SAE is essential so that legal obligations and ethical responsibilities towards the safety of participants and the safety of a study treatment under clinical investigation are met.
- The Sponsor has a legal responsibility to notify both the local regulatory authority and other regulatory agencies about the safety of a study treatment under clinical investigation. The Sponsor will comply with country-specific regulatory requirements relating to safety reporting to the regulatory authority, Institutional Review Boards (IRBs)/ Ethics Committees (ECs), and Investigators.
- An Investigator who receives an Investigator safety report describing an SAE or other specific safety information (eg, summary or listing of SAEs) from the Sponsor will review and then file it along with the IB and will notify the IRB/EC, if appropriate, according to local requirements.

11.7.5 Pregnancy

- Details of all pregnancies in female participants and, if possible, female partners of male participants will be collected after the start of study treatment and until the end of the study.
- If a pregnancy is reported, the Investigator will record pregnancy information on the appropriate form and submit it to the Sponsor within 24 hours of learning of the female participant or female partner of male participant (after obtaining the necessary signed informed consent from the female partner) pregnancy.
- While pregnancy itself is not considered to be an AE or SAE, any pregnancy complication or elective termination of a pregnancy for medical reasons will be reported as an AE or SAE.
- Abnormal pregnancy outcomes (eg, spontaneous abortion, fetal death, stillbirth, congenital anomalies, ectopic pregnancy) are considered SAEs and will be reported as such.

- The participant/pregnant female partner will be followed to determine the outcome of the pregnancy. The Investigator will collect follow-up information on the participant/pregnant female partner and the neonate and the information will be forwarded to the Sponsor.
- Any female participant who becomes pregnant while participating in the study will discontinue study treatment or be withdrawn from the study.

11.7.6 Adverse Events of Special Interest

There are currently no known adverse events of special interest for ATH-399A.

11.8 Pharmacokinetics

11.8.1 Plasma Pharmacokinetics

Plasma concentrations of ATH-399A (and metabolite identification only in Part 1a) will be determined by validated method(s).

Parts 1a and 1b PK parameters:

- AUC_{0-t} : Area under the concentration-time curve from time zero until the last observed concentration
- $AUC_{0-\infty}$: Area under the concentration-time curve from time zero to infinity (extrapolated)
- Residual area: Percentage of $AUC_{0-\infty}$ due to extrapolation from the time of the last observed concentration to infinity, calculated as $[1 - (AUC_{0-t}/AUC_{0-\infty})] \times 100$
- C_{max} : Maximal observed concentration
- T_{max} : Time when the maximal concentration is observed
- For Part 1b only: T_{lag} : Time of observation prior to the first observation with a measurable (non-zero) concentration.
- $t_{1/2 el}$: Terminal elimination half-life
- λ_z : Terminal elimination rate constant
- Cl/F : Apparent clearance
- V_z/F : Apparent volume of distribution

Part 2 PK parameters:

For Day 1, the following PK parameters will be calculated:

- AUC_{0-24} : Area under the concentration-time curve from time zero to time 24 hours
- C_{max} : Maximal observed concentration
- T_{max} : Time when the maximal concentration is observed

For Day 12, the following PK parameters will be calculated:

- $AUC_{0-\tau}$: Area under the concentration-time curve for one dosing interval (τ) at steady-state. In this study, $\tau = 24$ hours (AUC_{0-24})
- AUC_{0-t} : Area under the concentration-time curve from time zero until the last observed concentration
- $AUC_{0-\infty}$: Area under the concentration-time curve from time zero to infinity (extrapolated)
- $C_{max\ ss}$: Maximal observed concentration at steady-state
- $T_{max\ ss}$: Time when the maximal concentration is observed at steady-state
- $C_{min\ ss}$: Minimal observed concentration at steady-state
- Residual area: Percentage of $AUC_{0-\infty}$ due to extrapolation from the time of the last observed concentration to infinity, calculated as $[1 - (AUC_{0-t}/AUC_{0-\infty})] \times 100$
- $t_{1/2\ el}$: Terminal elimination half-life
- λ_z : Terminal elimination rate constant
- Cl_{ss}/F : Apparent clearance at steady-state
- $V_z\ ss/F$: Apparent volume of distribution at steady-state
- AR=accumulation ratio

Blood PK sample collection will be performed at the timepoints in [Table 6](#).

Table 6: Pharmacokinetic Blood Sample Collection Timepoints

Visit Day	Timepoint	Part 1a	Part 1b	Part 2
Day 1 of each Period/Cohort	Pre-dose (within 2 hours of dosing)	X	X	X
	0.25 hours (± 2 min) post-Day 1 dose	X	X	X
	0.5 hours (± 2 min) post-Day 1 dose	X	X	X
	1 hour (± 5 min) post-Day 1 dose	X	X	X
	1.5 hour (± 5 min) post-Day 1 dose	X	X	X
	2 hours (± 5 min) post-Day 1 dose	X	X	X
	3 hours (± 10 min) post-Day 1 dose	X	X	X
	4 hours (± 10 min) post-Day 1 dose	X	X	X
	6 hours (± 10 min) post-Day 1 dose	X	X	X
	8 hours (± 10 min) post-Day 1 dose	X	X	X
	12 hours (± 10 min) post-Day 1 dose	X	X	X
	16 hours (± 30 min) post-Day 1 dose	X	X	X
Day 2 of each Period/Cohort	24 hours (± 30 min) post-Day 1 dose	X	X	X
	36 hours (± 30 min) post-Day 1 dose	X	X	X
Day 3 of each Period/Cohort	48 hours (± 30 min) post-Day 1 dose	X	X	
Day 4 of each period	72 hours (± 1 hour) post-Day 1 dose (outpatient visit)	X (Cohorts 4 and 5 only)	X	
Day 5 of each period	96 hours (± 1 hour) post-Day 1 dose (outpatient visit)	X (Cohorts 4 and 5 only)	X	

Visit Day	Timepoint	Part 1a	Part 1b	Part 2
Day 9 of each Cohort	Pre-dose (within 2 hours of dosing)			X
Day 10 of each Cohort	Pre-dose (within 2 hours of dosing)			X
Day 11 of each Cohort	Pre-dose (within 2 hours of dosing)			X
Day 12 of each Cohort	Pre-dose (within 2 hours of dosing)			X
	0.25 hours (± 2 min) post-Day 12 dose			X
	0.5 hours (± 2 min) post-Day 12 dose			X
	1 hour (± 5 min) post-Day 12 dose			X
	1.5 hour (± 5 min) post-Day 12 dose			X
	2 hours (± 5 min) post-Day 12 dose			X
	3 hours (± 10 min) post-Day 12 dose			X
	4 hours (± 10 min) post-Day 12 dose			X
	6 hours (± 10 min) post-Day 12 dose			X
	8 hours (± 10 min) post-Day 12 dose			X
	12 hours (± 10 min) post-Day 12 dose			X
	16 hours (± 30 min) post-Day 12 dose			X
Day 13 of each Cohort	24 hours (± 30 min) post-Day 12 dose			X
	36 hours (± 30 min) post-Day 12 dose			X
Day 15 of each Cohort	72 hours (± 1 hour) post-Day 12 dose			X
Day 16 of each Cohort	96 hours (± 1 hour) post-Day 12 dose			X

An additional aliquot may be collected at each time point and stored for future evaluation of ATH-399A metabolites. Any blood samples drawn beyond the specified window period will be noted as early or late draws and will be recorded appropriately as a protocol deviation. A comment and explanation should be provided in the source documents. The exact collection time will be recorded in the source documents.

For Part 2: plasma concentration observed before treatment administrations (C_{trough}) during repeated dosing (Day 9, Day 10, Day 11 and Day 12) will be presented. In the additional cohort of participants >55 - 80 years of age (inclusive), future research and analysis of biomarkers may be performed using the residual samples originally collected for PK analysis required in this study. These analyses will only be performed if participants provided specific additional consent.

Refer to the Analytical Methodology Information Sheet (AMIS) for the collection, processing, and shipping of PK samples.

11.8.2 Urine Pharmacokinetics

In Part 1a, urine samples will be collected for analysis of ATH-399A concentrations and identification of metabolites at pre-dose, and at the following time intervals: 0-4 hours, 4-8 hours, 8-12 hours, 12-24 hours, and 24-48 hours post-dose.

If a participant cannot void their bladder within 30 minutes before dosing, a urine sample from an earlier morning urine collection may be used as the pre-dose sample. Voids that occur within the time interval will be pooled, and participants will be asked to void their bladder within 30 minutes before the end of each collection interval, so that each new interval will begin with an empty bladder. Any urine voided by participants at the intersection (within 10 minutes) of two intervals will be included in the earlier sample. Any urine voided by participants but not collected will be documented. If a participant is unable to void at the end of a collection interval, the unsuccessful attempt will be documented.

Refer to the AMIS for the collection, processing, and shipping of urine samples.

For Part 1a, the following PK parameters will be calculated for [ATH-399A and metabolite(s), if applicable] urine concentrations:

- Ae_{0-t} : Cumulative urinary excretion from time zero to time t , calculated as the sum of the amounts excreted over each collection interval
- R_{max} : Maximal rate of urinary excretion, calculated by dividing the amount of drug excreted in each collection interval by the time over which it was collected
- T_{Rmax} : Time of maximal urinary excretion, calculated as the midpoint of the collection interval during which R_{max} occurred
- Cl_R : Renal clearance, calculated as Ae_{0-t}/AUC_{0-t}

Additional PK parameters may be calculated.

12 STATISTICAL CONSIDERATIONS

The Statistical Analysis Plan (SAP) will be finalized prior to database lock, and it will include a more technical and detailed description of the statistical analyses described in this section. This section is a summary of the planned statistical analyses.

12.1 Analysis Sets

For the purposes of analysis, the following analysis sets are defined:

- The Safety Population includes all participants who received at least one dose of study medication, ATH-399A or placebo.
- The Pharmacokinetic (PK) Population includes all participants who received at least one dose of ATH-399A, and provided at least one plasma or urine concentration measure.

12.2 General Considerations

All collected data will be reported using summary tables and figures, as appropriate. Data summaries will be presented separately by part, dose, cohort, and overall. Tabulations will be produced for appropriate disposition, demographic, baseline, safety, and PK parameters. Categorical variables will be summarized by frequency distributions (number and percentages of participants) and continuous variables will be summarized by descriptive statistics (mean, standard deviation, median, minimum, and maximum). As appropriate, a 95% confidence interval (CI) will be presented. Graphical displays will be presented, as appropriate. All data will be provided in by-participant listings.

Baseline is defined as the last value prior to the first dose and will be flagged for all necessary analyses.

12.3 Disposition and Baseline Characteristics

Participant disposition will be tabulated by part, cohort, treatment assignment, and dose. Disposition will include the number and percent of participants who are enrolled, those who receive treatment, discontinue early, with reasons for discontinuation, and completers. Summary statistics will be reported for baseline characteristics by cohort, part, treatment assignment, and dose.

12.4 Safety Analyses

Safety and tolerability of ATH-399A will be evaluated through the assessment of AEs (i.e., seriousness, severity, relationship to the study drug, outcome, duration, and management), vital signs, 12-lead ECGs, clinical laboratory tests, and physical examinations. AEs will be coded using the latest version of the MedDRA dictionary.

Demographic parameters will be summarized descriptively.

Safety and tolerability analysis will be performed for all participants in the safety population. No inferential statistical analysis of safety data is planned.

AEs and SAEs, will be tabulated by treatment. Changes from baseline values in vital signs, 12-lead ECGs, and clinical laboratory tests will be evaluated. Safety and tolerability data will be reported using descriptive statistics.

12.5 Pharmacokinetic Analyses

Plasma and urine concentrations of ATH-399A will be tabulated descriptively by sampling time-point. Plasma pharmacokinetic parameters will be calculated by non-compartmental methods. Descriptive statistics (n, arithmetic mean, SD, minimum, median, maximum, coefficient of variation [CV], geometric mean and geometric CV) of the plasma PK parameters will be provided by part, dose, and cohort. Individual and mean plasma concentration-time profiles will be presented graphically on both linear and semi-logarithmic scales for each dose level using nominal time points.

For Part 1a, summary statistics will be used to describe the PK profile of [ATH-399A and metabolite(s), if applicable] for each dose level. The power model approach will be performed on AUC_{0-t} , AUC_{0-inf} , and C_{max} data to assess the dose-proportionality. An ANOVA will also be performed on the untransformed T_{max} , $t_{1/2 el}$, and λ_z data.

Part 1b (food effect) will be evaluated by analysis of variance, with terms for participant, sequence, period, treatment as fixed effects and participant within sequence as a random effect for the ATH-399A parameters C_{max} and AUC_{0-t} and AUC_{0-inf} . The exposure measurements (AUCs and C_{max}) will be log-transformed prior to analysis. The 90% CI for the ratio of population geometric means between test (fed) and reference products (fasting) will be provided for AUC_{0-t} and AUC_{0-inf} and C_{max} . Intra- and inter-subject CV will also be estimated.

For Part 2, summary statistics will be used to describe the PK profile of [ATH-399A and metabolite(s), if applicable] for each dose level. The power model approach will be performed on C_{max} , AUC_{0-tau} , $C_{max ss}$, $C_{min ss}$, AUC_{0-t} , and AUC_{0-inf} data to assess the dose-proportionality. An ANOVA will also be performed on the untransformed T_{max} , $T_{max ss}$, $t_{1/2 el}$, and λ_z data. Repeated measures analysis will be carried out on ln transformed pre-dose concentrations (Days 9 to 12) to determine attainment of steady-state. Comparisons between Day 1 and Day 12 PK parameters: AUC_{0-24} versus AUC_{0-t} , C_{max} versus $C_{max ss}$, and T_{max} versus $T_{max ss}$ will be done by ANOVA. Ratios (Day 12/Day 1) and 90% geometric CI will be computed for AUC and C_{max} .

12.6 Interim Analyses

There are no planned interim analyses for this study. Safety and PK summaries will be available for SRC meetings.

12.7 Sample Size Determination

The sample size for each stage was determined based on standard practice in Phase 1 food effect, SAD and MAD studies empirically and was not powered for statistical significance. Cohort sizes were selected based on those commonly utilized in similar Phase 1 studies and thus generally considered sufficient to assess safety, tolerability, and estimate PK parameters.

13 SUPPORTING DOCUMENTATION AND OPERATIONAL CONSIDERATIONS

13.1 Appendix 1: Regulatory, Ethical, and Study Oversight Considerations

13.1.1 Regulatory and Ethical Considerations

- This study will be conducted in accordance with the protocol and with the following:
 - Consensus ethical principles derived from international guidelines including the Declaration of Helsinki and Council for International Organizations of Medical Sciences (CIOMS) international ethical guidelines
 - Applicable ICH GCP guidelines
 - Applicable laws and regulations
- The protocol, protocol amendments, ICF, IB, and other relevant documents (eg, advertisements) must be submitted to an IRB/EC by the Investigator and reviewed and approved by the IRB/EC before the study is initiated.
- Any amendments to the protocol will require IRB/EC approval before implementation of changes made to the study design, except for changes necessary to eliminate an immediate hazard to study participants.
- Protocols and any substantial amendments to the protocol will require health authority approval prior to initiation except for changes necessary to eliminate an immediate hazard to study participants.
- The Investigator will be responsible for the following, as applicable:
 - Providing written summaries of the status of the study to the IRB/EC annually or more frequently in accordance with the requirements, policies, and procedures established by the IRB/EC
 - Notifying the IRB/EC of SAEs or other significant safety findings as required by IRB/EC procedures
 - Providing oversight of the conduct of the study at the site and adherence to requirements of 21 CFR, ICH guidelines, the IRB/EC, and all other applicable local regulations

13.1.2 Financial Disclosure

Investigators and sub-investigators will provide the Sponsor with sufficient, accurate financial information as requested to allow the Sponsor to submit complete and accurate financial certification or disclosure statements to the appropriate regulatory authorities. Investigators are responsible for providing information on financial interests during the course of the study and for 1 year after completion of the study.

13.1.3 Informed Consent Process

The Investigator agrees to provide the IEC with all appropriate documents, including a copy of the protocol/amendments, ICFs, advertising text (if any), IB, and any other written information provided to study participants. The trial will not begin until the Investigator have obtained the IEC favourable written approvals for the above-mentioned study documents. A properly executed written ICF shall be read, signed, and dated by each participant prior to entering the trial or prior to performing any study procedure. The original signed and dated ICF will be kept at the clinical site and a copy will be given to the participant.

In the event that the protocol is amended, the revised protocol must be approved by the IEC prior to its implementation, unless the changes involve only logistical or administrative aspects of the trial. If a revised ICF is introduced during the study, each participant's further consent must be obtained. The new version of the ICF must be approved by the IEC, prior to subsequently obtaining each participant's consent.

The Investigator and the Sponsor's representative must sign the protocol and its amendments (if any) before initiating the study.

It is the Sponsor's responsibility to submit the protocol and its amendments (if any), and the ICFs to regulatory authorities when necessary.

13.1.4 Data Protection

- Randomized participants will be assigned a unique identifier by the Sponsor. Any participant records or datasets that are transferred to the Sponsor will contain the identifier only; participant names or any information which would make the participant identifiable will not be transferred.
- The participant must be informed that their personal study-related data will be used by the Sponsor in accordance with local data protection law. The level of disclosure must also be explained to the participant who will be required to give consent for their data to be used as described in the informed consent.
- The participant must be informed that their medical records may be examined by Clinical Quality Assurance auditors or other authorized personnel appointed by the Sponsor, by appropriate IRB/EC members, and by inspectors from regulatory authorities.
- The contract between Sponsor and study sites specifies responsibilities of the parties related to data protection, including handling of data security breaches and respective communication and cooperation of the parties.
- Information technology systems used to collect, process, and store study-related data are secured by technical and organizational security measures designed to protect such data against accidental or unlawful loss, alteration, or unauthorized disclosure or access.

13.1.5 Committees Structure

13.1.5.1 Safety Review Committee

An SRC will be established to review safety and any available PK data and to oversee the overall conduct of the study with the primary purpose of protecting the safety of participants participating in the study. Details concerning the specific objectives, roles, responsibilities, and data review procedures of the SRC are documented in a separate SRC Charter document. The SRC will be composed of at least the Investigator, one medically qualified Sponsor representative and an independent MM.

The SRC may consult with or add members that include, but are not limited to, physician(s) scientists, biostatisticians, or other subject matter experts.

The SRC will meet as soon as is feasible, upon the occurrence of safety signals and after completion of dosing a given cohort to recommend acceptability of continued dosing, as well as escalation, de-escalation, or whether to add additional participants at the current dose level.

All data (reports) that are provided and reviewed by the SRC, including any minutes and decisions from the meetings, will be archived. The minutes will document clearly any questions posed and decisions reached and whether these decisions were unanimous.

SRC meetings will be held after safety and tolerability data up to at least 48 hours post-dose (Day 3) are available for at least 6 evaluable dosed participants from a same cohort for the SAD part, and after safety and tolerability data up to at least 24 hours post-last dose (Day 12) are available for all dosed evaluable participants from a same cohort for the MAD part. PK data up to 24 hours post-dose (post-last dose for the MAD part) will also be reviewed to evaluate if PK parameters in humans are as anticipated. The SRC will consider the data on a cohort basis, but also on the basis of cumulative information across cohorts as the study progresses.

The potential decisions of the SRC are:

- Escalate to the next planned dose level;
- Continue the study with a more conservative approach, such as decreasing to a dose-level lower than the planned next higher dose level, descending from a higher dose level to a lower dose level, repeating a dose level, or exploring an alternative dosing regimen in the MAD part (not exceeding the total daily dose planned in the protocol for that given cohort);
- Suspend dose escalation until further review of study data can be made, allowing the SRC to determine whether predefined stopping rules have been met. Dose escalation may resume once the SRC concludes that no stopping rules have been met;
- Stop dose escalation;
- Terminate the study.

The SRC will conduct a blinded review of the data; however the blind may be broken for individual participants if judged necessary, prior to making a decision on dose escalation. Dose escalation may occur only following mutual agreement between the SRC members. The SRC may recommend to modify the PK sample collection schedule based on emerging data, including shortening or lengthening the total collection interval by up to 48 hours, and may add up to two additional PK samples, if necessary. Decisions taken by the SRC will be documented and submitted to the IEC overseeing the study, if required, along with supportive data.

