The study will be monitored by an SRC. The SRC is intended to ensure that treatment does not pose undue risk to participants. The SRC will be composed of at least the Investigator, one medically qualified Sponsor representative and an independent Medical Monitor (MM). SRC meetings will be held after safety and tolerability data through follow-up visit for at least 6 dosed participants from a same cohort and PK data up to at least 48 hours post-dose (Day 3 for Parts 1a and 1b) and 24 hours post-last dose (Day 13 for Part 2) from a same cohort are available. The SRC will consider the data on a cohort basis, but also on the basis of cumulative information across cohorts as the study progresses. The SRC recommendations should be based on results from a minimum of 6 evaluable participants in each dosing cohort.

Safety/tolerability data through the final follow-up visit for each of the 6 evaluable participants in a cohort along with PK data up to at least 48 hours post-dose in Part 1a and 1b (or 24 hours post-last dose in Part 2) will be assessed by the SRC prior to:

- a. Ascending from one dose-level cohort to the next higher dose level cohort in Parts 1a and 2,
- b. Prior to transitioning from Part 1a to Parts 1b and 2.

The SRC will stop dose escalation or descend to a dose level lower than the planned next higher dose level if any of the following criteria are met:

- One participant per cohort who receives ATH-399A experiences a serious adverse event (SAE) which is considered to be related to the study medication.
- Two participants per cohort who receive ATH-399A have QTc prolongation, defined as an average absolute (regardless of baseline value) QTcF >500 msec or an increase of QTcF > 60 msec above baseline, confirmed by repeating after 5 minutes, and determined post-dose.
- Two participants per cohort who receive ATH-399A exhibit hypotension, defined as resting supine diastolic blood pressure <40 mmHg persisting for at least 10 minutes on repeated assessment, or an asymptomatic or symptomatic fall in systolic blood pressure to below 80 mmHg, persisting for at least 10 minutes on repeated assessment.
- Two participants per cohort who receive ATH-399A exhibit hypertension, defined as an increase in resting systolic blood pressure to above 180 mmHg, persisting for at least 10 minutes, or an increase in resting diastolic blood pressure to above 105 mmHg, persisting for at least 10 minutes.

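### For Part 1a, Appendix 13.1.5.1 sets a lower data floor for SRC meetings that may decide to escalate than the synopsis and Section 7.3 do

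*Protocol*

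**What the plan says.** Two parts of the current protocol define when the SRC meets, in nearly the same words, and they differ for Part 1a.

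**Appendix 13.1.5.1.** The SRC meets on safety signals and "after completion of dosing a given cohort to recommend acceptability of continued dosing, as well as escalation". For the single-dose part, "SRC meetings will be held after safety and tolerability data up to at least 48 hours post-dose (Day 3) are available"; the headcount is 6 or more evaluable dosed participants of a cohort. On exposure, "PK data up to 24 hours post-dose (post-last dose for the MAD part) will also be reviewed", with no minimum. The first decision listed is "Escalate to the next planned dose level". The same section adds: "Dose escalation may occur only following mutual agreement between the SRC members". It refers to a separate SRC charter for review procedures.

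**Synopsis, SRC and dose escalation criteria.** "SRC meetings will be held after safety and tolerability data through follow-up visit for at least 6 dosed participants from a same cohort", together with "PK data up to at least 48 hours post-dose (Day 3 for Parts 1a and 1b").

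**Section 7.3.** The visible text requires safety through the final follow-up visit for each of 6 evaluable participants, plus PK to at least 48 hours in Part 1a, before ascending to the next cohort. The opening of 7.3 is not visible. The attribution rests on the table of contents and on the match with the synopsis text.

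**Section 7.1.1.** Safety through the follow-up visit for at least 6 evaluable participants, but PK only for up to 48 hours. So only the synopsis SRC text and 7.3 make 48 hours a minimum for PK.

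For Part 2 the appendix has "24 hours post-last dose (Day 12) are available for all dosed evaluable participants" and does not mention the follow-up visit. The synopsis puts the same time point on Day 13.

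**The concern.** Part 1a is the first exposure of humans to ATH-399A, and each step doubles the dose. The data required before a step are the main procedural protection for the next cohort, so they should be stated once or identically everywhere.

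What lies between the two cut-offs matters. In Table 1 the follow-up visit holds the only scheduled chemistry and hematology after the Day 3 (48-hour) sample. The Day 4 and Day 5 outpatient visits, in Cohorts 4 and 5 only, add scheduled PK blood and no safety laboratory tests. Abnormal liver tests in a single participant on active drug are enough to stop escalation, and a rise that appears after Day 3 would not yet have been looked for. Follow-up also holds the only scheduled post-dose C-SSRS in Part 1a, and C-SSRS is a named component of the primary safety endpoint.

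**Working it through.** The plan gives no figure to reproduce. The check is a comparison of the texts plus day counts.

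**1. Requirements side by side, Part 1a**

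| Item | Appendix 13.1.5.1 | Synopsis SRC text and 7.3 | Difference |
|---|---|---|---|
| Safety cut-off | at least 48 h (Day 3) | follow-up visit (Day 8 to 11) | 8 − 3 = 5 to 11 − 3 = 8 days |
| PK cut-off | up to 24 h, no minimum | at least 48 h | 48 − 24 = 24 h |
| Participants | at least 6 evaluable | at least 6 (7.3: evaluable) | none |
| Escalation covered? | yes, a listed decision | yes (7.3: prior to ascending) | none |

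**2. Decisions affected.** 5 to 10, 10 to 20, 20 to 40 and 40 to 80 mg: up to 4.

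**3. Who has been followed up when the appendix floor is first met?** Let the sentinels be dosed on calendar Day 1 and the other 6 together at the minimum wait.

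- 48 h wait (Protocol 7.1.1 and 9.7): the others are dosed on calendar Day 3 and reach their own Day 3 on calendar Day 5.
- 96 h wait (SAP 3.3.1, Cohorts 4 and 5): the others are dosed on calendar Day 5 and reach their own Day 3 on calendar Day 7.

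Sentinel follow-up opens on calendar Day 8, after both dates. So 0 of 8 have follow-up data if the meeting is held at once.

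**4. Sensitivity to delay.** The documents give no turnaround time. Let the meeting come *d* days after the floor is met, to allow for PK assay, data preparation and scheduling. The shortfall is then 5 − *d* to 8 − *d* days, not below zero.

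- *d* = 0: 5 to 8 days, 0 of 8 followed up.
- *d* = 3 with the 48 h wait (5 + 3 = 8) or *d* = 1 with the 96 h wait (7 + 1 = 8): the 2 sentinels could have been seen, so at most 2 of 8.
- *d* = 5: the non-sentinels reach their own Day 8 (calendar Day 10 or 12). Only then can 6 participants have follow-up data.

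So 0 of 8 gives way after a short delay, but the minimum of 6 cannot be met until *d* reaches 5.

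**5. PK samples.** Post-dose times to 48 h: 0.25, 0.5, 1, 1.5, 2, 3, 4, 6, 8, 12, 16, 24, 36 and 48 h, which is 14. To 24 h there are 12. The 36 h and 48 h samples fall outside the appendix review. The AUC over 0 to 24 h, which has its own stopping threshold, can still be calculated.

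**6. Part 2.** The last dose is on Day 12, so 24 h later is Day 13. Section 7.1.3 puts Cohort 2 about 3.5 × 7 = 24.5 days after the first Cohort 1 dose, near Day 25.5. If Cohort 1 is dosed on one day, that is 25.5 − 22 = 3.5 to 25.5 − 19 = 6.5 days after its follow-up visit. The PK cut-off matches 7.3.

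**The case against.** The best case against is that the escalation condition is already explicit. Section 7.3 lists what must be assessed before ascending, and 7.1.1 and the synopsis repeat the follow-up requirement. The appendix says at least 48 hours, which is a floor for SRC meetings in general, including safety-signal meetings, so a meeting after follow-up satisfies both safety rules. The Investigator sits on the SRC, the whole protocol binds, escalation needs the members' mutual agreement, and the charter may settle the matter. Adverse events are also collected continuously, so a symptomatic event between Day 3 and follow-up could be known.

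Much of this stands. A reader might infer that the appendix fixes escalation at Day 3, or that it displaces 7.3. The documents support neither: the appendix wording is a minimum, and nothing gives it precedence. A reader might also take 5 to 8 days as the expected loss. It is a limiting case, because PK results must be in hand before the review and no turnaround is given. The PK difference is minor.

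What remains is that compliance runs one way only. Following 7.3 meets the appendix safety floor, but following the appendix does not meet 7.3. The appendix paragraph cannot be confined to ad hoc meetings, since it covers the meeting after a cohort is dosed and lists escalation among its decisions. No visible text says which section prevails. Mutual agreement governs who must consent, not which data they must hold. The charter was not available, so it cannot be assumed to resolve the difference.

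**Conclusion.** The inconsistency is real and should be fixed. For Part 1a, the appendix would allow an SRC relying on it alone to escalate on data that the synopsis and 7.3 do not accept. The textual conflict is certain. Whether an early escalation would follow is not, because it requires the SRC to overlook 7.3.

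The worst case is 5 to 8 days less follow-up per participant at each of up to 4 steps, with 0 of 8 followed up. It rests on a meeting as soon as the floor is met, non-sentinels dosed together at the minimum wait, and no PK turnaround. Each day of delay takes a day off the shortfall.

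A reader might extend the point to Part 2, because the appendix omits the follow-up visit there too. The documents do not support a claim of early escalation: the stated interval of about 3.5 weeks places Cohort 2 after Cohort 1 follow-up if that cohort is dosed on one day, and the appendix already asks for all dosed evaluable participants. For Part 2 the clear error is the day label.

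**What to change.** In 13.1.5.1, replace the meeting gate with: *SRC meetings to decide on escalation will be held only when the safety and PK data required by Section 7.3 are available; earlier ad hoc meetings for safety signals may not decide to escalate.* Correct the Part 2 label for 24 hours after the last dose from Day 12 to Day 13. Check that the SRC charter sets the same condition.

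A cross-reference is safer than restating the cut-offs, because it leaves one source. This change should not add a Part 2 participant requirement beyond the minimum of 6 in 7.3. If the sponsor wants a stricter one, it should be decided in 7.3.

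The cost is one appendix paragraph and a charter check, with no added visits, samples or waiting time beyond what 7.3 already requires.

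The sentinel differences between SAP and protocol are a separate item: the 96-hour wait in SAP 3.3.1 against 48 hours in Protocol 7.1.1, and unconditional Part 2 sentinels in SAP 3.4 against conditional ones in Protocol 9.7.
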